#### **4.1 Substudies (if applicable)**

Not Applicable

## **5 STUDY POPULATION**

Enrollment will be confined to women 18 years of age and older who are nonpregnant and have active genital HSV lesions (Group 1, n=300) or women 19 years of age and older who are pregnant and do not have visible genital HSV lesions or prodromal symptoms (Group 2, n=12,500). Women of all races will be included.

### **5.1 Recruitment Strategies**

Identification of study subjects will be done based on the local standards of practice and IRB approved means. Clinicians who are care providers for these patients will identify patients who would generally qualify for inclusion in Group 1 or Group 2 of the study and will confirm that it is acceptable by the patient for the research team to approach them to discuss inclusion in the study. Group 1 subjects will be recruited from the STI clinic at the Health Department and/or similar outpatient facility. Group 2 subjects will be recruited from labor and delivery facilities and/or identified through obstetric practices. Subjects can sign informed consent in the labor and delivery facilities, or can sign informed consent prior to that time if the woman is 34 weeks estimated gestational age or older. However, no study related samples/procedures can be initiated until subject is admitted to the hospital labor and delivery area with the intent of delivering her baby. Each participating facility will determine the appropriate setting from which to recruit subjects. IRB approval will be obtained for each site's recruitment plan. Site investigators (who may also be the treating clinician) or study coordinators will provide information about the intended study population to the clinicians to aid in identifying appropriate patients to be approached for inclusion and consent. Consenting will be conducted by the research team (e.g., investigator and/or study coordinator/trained designee) for Group 1 and Group 2. Informed consent will be obtained prior to any study required procedures. The State of Alabama has recently (2015) changed the age of consent from 19 years to 18 years. As a result, Group 1 (which is still enrolling at the time of amendment of the protocol to version 4.0) will now enroll women who are 18 years of age or older. Recruitment and enrollment into Group 2 is not affected by this change because the cohort is already fully enrolled.

### **5.2 Subject Inclusion Criteria**

- Signed Informed Consent from woman
- $\geq 18$  years of age (Group 1);  $\geq 19$  years of age (Group 2)
- Female gender

- Group 1: women not known to be pregnant and being evaluated in STI clinics for herpetic genital lesions; OR Group 2: pregnant women  $\geq$  34 weeks estimated gestational age

### **5.3 Subject Exclusion Criteria**

- For women in Group 2 (pregnant women admitted with the intent of delivery), active herpetic lesions or prodromal symptoms in the genital region
- Receipt of acyclovir, valacyclovir, or famciclovir within the previous 14 days
- Known HIV infection

## **6 STUDY PROCEDURES/EVALUATIONS**

### **6.1 Test Device**

The Xpert HSV1/2 Assay, performed on the GeneXpert Instrument Systems, is a new qualitative *in vitro* PCR test for the automated and rapid detection and qualitative differentiation of HSV 1 and HSV 2 in clinician-collected genital swabs. The Xpert HSV1/2 Assay system performs multiplex polymerase chain reaction (PCR) for detection of DNA targets after an initial sample processing step. The system consists of a GeneXpert® instrument, personal computer, and disposable fluidic cartridges that are designed to complete sample preparation and real-time PCR for detection of HSV1 and/or HSV2 in about 1 hour.

The single-use cartridges contain: 1) eleven chambers for holding sample, reagents, or other materials; 2) a valve body composed of a plunger and syringe barrel; 3) a rotary valve system for controlling the movement of fluids between chambers; 4) an area for capturing, concentrating, washing, and lysing of virus; 5) dry, real-time PCR reagents; 6) liquid reagents for PCR; and 7) an integrated PCR reaction tube that can be automatically filled by the instrument. To eliminate test-to-test contamination, all fluids including amplicons are contained within the disposable cartridge. The instrument never comes into contact with any fluids within the cartridge. Each cartridge is intended to test one sample.

The primers and probes in the Xpert HSV1/2 Assay detect and differentiate HSV-1 and HSV-2 DNA sequences. Each test cartridge includes a Sample Processing Control (SPC), a Sample Adequacy Control (SAC), and a Probe Check Control (PCC). The SPC is present to control for adequate processing of the target bacteria and to monitor the presence of inhibitors in the PCR reaction. The SAC reagents detect the presence of a single copy human gene and monitor whether the sample contains human DNA. The PCC verifies reagent rehydration, PCR tube filling in the cartridge, probe integrity, and dye stability.

Cepheid (Sunnyvale, CA) will provide the GeneXpert system (instrument and cartridges). Xpert HSV 1/2 Assay cartridges will be appropriately labeled in accordance with regulations, and will be stored as indicated in the package insert. The UAB Central Laboratory personnel will be responsible for maintaining logs of receipt, accountability, storage conditions of the Xpert HSV 1/2 Assay investigational device and associated records and results. Documents and the investigational device will be stored in a secure and accessible location.

### **6.2 Study Procedures**

If a patient is eligible for the study based on information regarding inclusion/exclusion criteria that is collected as part of the standard medical care (and not obtained for study purposes), then

the clinical team, following consultation with the patient indicating that she is interested to hear more about the study, will contact the study staff who will approach the patient and initiate the informed consent process (Section 11). For Group 1, signing of the informed consent document will take place on the same day as study procedures. For Group 2, signing of the informed consent document may occur on or before Study Day 1. Patients may be provided with study information prior to confirmation of eligibility for enrollment. After consent is obtained, the study participant will begin participation in the study procedures.

Following informed consent and confirmation of eligibility criteria, virologic sampling will be obtained from women in Group 1 and Group 2. No laboratory tests will be done to confirm eligibility. For the Group 1 women (nonpregnant women with active genital HSV lesions), a swab of the lesion(s) will be obtained and placed in viral transport media. For the Group 2 women (pregnant women without active lesions), following admission to the hospital labor and delivery area with the intent of delivering her baby a swab of the vaginal vault/canal will be obtained and placed in viral transport media; utilization of a speculum examination is not required in this sampling process. The specimen should be obtained before delivery, but may be obtained following delivery as long as it is collected within 24 hours following delivery. Women in both Groups 1 and 2 will have a venipuncture for collection of blood for serologic testing. This test will be performed only if the subject's virologic studies identify HSV shedding.

Women in Group 2 will be provided with printed material describing neonatal HSV signs and symptoms. These women (Group 2) or their designated representative also will be contacted between Study Day 30 and Study Day 90 for self-reporting of the delivery mode (vaginal vs. Cesarean delivery) and the development of neonatal HSV symptoms and signs post-delivery. It is acceptable to initiate contact shortly following the 30 day window and multiple attempts may be needed to reach the mother or her designated representative. The initial maternal Informed Consent document will include obtaining parental permission for the neonate in order to ask these questions. Verbal reporting from the mother on maternal receipt of antiviral therapy at any point following enrollment also will be captured from all women in Group 2.

HSV culture results (not PCR) from women in Group 1 will be reported to their treating physician. Virologic results from women in Group 2 will not be reported back to the subject or her physician. The reasons for not reporting results to the Group 2 subject or her physician are two-fold: 1) the PCR analyses are performed in batches, so no results will be available within a timeframe in which clinical decisions on the woman's care could be made; and 2) neither routine HSV PCR nor Xpert HSV 1/2 Assay are FDA-cleared for evaluation of HSV testing on women without active lesions, and thus the reliability of a positive or a negative test result in this population is not known. Even if PCR results (routine HSV PCR or Xpert HSV 1/2 Assay) could be obtained in a real-time (non-batched) fashion, it would be irresponsible to report results from a non-validated test to the subject and her health care provider, as they may be influenced to make clinical decisions based on this unvalidated information. Furthermore, using the results of this research test for clinical decision making is not the intent of this study protocol.

Subjects are not required to be seen in person after their involvement on Study Day 1. However, for Group 2 study staff may visit or contact the subject before she is discharged from the hospital to confirm the follow-up contact information. No additional contact is made with the subject following Study Day 1 for Group 1, and following the Study Day 30-90 contact for Group 2.

## **6.3 Laboratory Evaluations**

### **6.3.1 Laboratory Evaluations/Assays**

#### Virologic Testing

Samples obtained from women in Group 1 and Group 2 will be tested in batches for HSV DNA by Xpert HSV 1/2 PCR and routine PCR. Additionally, samples from women in Group 1 will be tested in real time by HSV culture. In this trial, all of these virologic tests will be Research Laboratory Evaluations (i.e., they would not be performed if the subject were not enrolled in the study). Routine HSV PCR from genital mucosa is not an FDA-cleared test. All Xpert and routine PCR testing will be conducted at the UAB CLIA-certified Central Laboratory. Bi-directional sequencing will be performed on specimens with discordant results between the Xpert HSV 1/2 PCR and routine PCR from asymptomatic pregnant women admitted with the intent of delivery, and between Xpert HSV 1/2 PCR and HSV culture in nonpregnant women. The primers used for bi-directional sequencing will be different from those used in the Xpert HSV 1/2 PCR and the routine PCR methods. Note: The results of discrepant analysis are for informational purposes only and will not be used to recalculate the performance of the Xpert HSV 1/2 PCR Assay.

#### Venipuncture

Women in both Groups 1 and 2 will have a venipuncture on Study Day 1 for collection of at least 0.5 mL of serum for serologic testing for HSV type-specific antibody. This serologic test will be performed for subjects in either group only if the subject's virologic studies identify HSV shedding. In this trial, all serologic tests will be Research Laboratory Evaluations (i.e., they would not be performed if the subject were not enrolled in the study). The window of time for collection of this specimen from women in Group 2 is  $\pm 3$  days. Remnant blood samples from clinical laboratory draws may be retrieved for this serologic testing. Informed consent will be obtained prior to any study required procedures.

## **6.3.2 Specimen Preparation, Handling, and Shipping**

### **6.3.2.1 Instructions for Specimen Preparation, Handling, and Storage**

Group 1: Lesion swabs from nonpregnant women in STI clinics will be placed in viral transport media, refrigerated at 2-8°C, and transported by the study coordinator or designee in real time to the laboratory for analysis by HSV culture in real time, and by Xpert HSV 1/2 PCR and routine HSV PCR (batched analysis at the UAB Central Laboratory).

Group 2: Vaginal swabs from pregnant women admitted with the intent of delivery will be placed in viral transport media, frozen at -20°C or colder, and batch-shipped to the UAB Central Laboratory for batched analysis by Xpert HSV 1/2 PCR and by routine HSV PCR. Only one freeze-thaw cycle will be required for each type of PCR test. Specimens will be assigned by the Study Biostatistician to either batched processing by routine PCR or to storage for possible testing by PCR in the future. Those that are batch processed by routine PCR also will be analyzed subsequently by Xpert HSV 1/2 PCR.

Serum from blood samples will be frozen at -20°C or colder and batch-shipped to the UAB Central Laboratory for HSV serologic testing. If remnant blood is retrieved for this purpose, it should have been stored according to local laboratory standard operating procedures until retrieval for research purposes.

Specific instructions on specimen preparation, handling, and shipping will be provided in the Manual of Procedures (MOP) for this study. Residual specimens will be stored at the UAB Central Laboratory if consent is provided by the study subject. Access to these specimens is detailed in Section 10.1.

### **6.3.2.2 Specimen Shipment**

Specific instructions on specimen shipments, including frequency and location, will be provided in the Manual of Procedures (MOP) for this study.

## **7 STATISTICAL CONSIDERATIONS**

### **7.1 Study Hypotheses**

For pregnant women, we hypothesize that the long term expected positive percent agreement of HSV DNA using the Xpert HSV 1/2 Assay is 95% as evidenced by confidence interval containing this value. Therefore, with a sample size of between 135 and 150 we will have over a 95% probability of obtaining a point estimate greater than 91.8% with a lower bound of a 95% CI greater than 85%. This can be summarized in the form of hypothesis testing as:

$H_0$ : Positive Percent Agreement = 95%

$H_A$ : Positive Percent Agreement < 85%

Sample Size 135-150

Critical Value = 11FN, (or point estimate > 91.85% with lower 95% CI > 85%)

Target Alpha Value = 5%, Power > 95%.

For non-pregnant women, we hypothesize that the long term expected sensitivity of HSV DNA using the Xpert HSV 1/2 Assay is 95.34% as evidenced by a 95% confidence interval containing this value. Therefore, with a sample size of between 270 and 300 we will have a 95% probability of obtaining a point estimate greater 93.3% with a lower bound of a 95% CI greater than 90%. This can be summarized in the form of hypothesis testing as:

$H_0$ : Sensitivity = 95.34%

$H_A$ : Sensitivity < 90%

Sample Size 270-300

Critical Value = 18 false negative (FN), (or point estimate > 93.3% with lower 95% CI > 89%)

Target Alpha Value = 5%, Power > 95%.

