### **7.2 Sample Size Considerations**

Approximately 6,000 pregnant women (of the 12,500 enrolled) admitted with the intent of delivery will be tested to detect 144 (2.4%) who are shedding HSV by PCR. A subject who enrolls on the study but does not have a vaginal specimen obtained will not count toward the target sample size. The process of determining the 6,000 to be tested by PCR is as follows: IDs of pregnant women enrolled in a given 3 month period (each quarter) will be randomly assigned by site to either (1) the group to be tested by PCR or (2) the group not to be tested by PCR. This will enable us to have better representation over time and across sites. Specimens will be collected and tested from an additional 300 nonpregnant women presenting to STI clinics with active herpetic lesions who are shedding HSV by both PCR and culture. A 95% confidence interval will be constructed for the sensitivity of Xpert HSV 1/2 Assay relative to culture for the nonpregnant women population. Since we do not anticipate many negative results in the

symptomatic nonpregnant population, we may not be able to estimate the specificity of the GeneXpert in this population. For the pregnant women population, 95% confidence intervals will be constructed for the true positive and negative percent agreement between Xpert and routine PCR. The sample size justification considers the width and lower bound of these 95% confidence intervals for a single proportion using Clopper-Pearson method (also known as the Fisher’s Exact CI) for small samples and large-sample confidence intervals for samples of greater than 100 (Ref Nonparametric Statistical Methods, Hollander and Wolf, Wiley, NY, NY 1973). SAS version 9.2 was used for these calculations.

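### Section 7.1 gives conflicting accuracy criteria and interval methods, and its 95% probability for Group 1 does not go with an exact lower limit above 90%

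*Combined protocol and SAP*

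**What the plan says.** Section 7.1 gives each group a target and a way of evidencing it. For Group 2, positive percent agreement "is 95% as evidenced by confidence interval containing this value". For Group 1, sensitivity "is 95.34% as evidenced by a 95% confidence interval containing this value".

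The same paragraphs then promise a probability of clearing a floor and a lower limit:

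- Group 2 (n=135 to 150): "we will have over a 95% probability of obtaining a point estimate greater than 91.8"%, together with a lower limit above 85%.
- Group 1 (n=270 to 300): a 95% probability of "obtaining a point estimate greater 93.3% with a lower bound of a 95% CI greater than 90"%.

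The hypothesis-test summaries add:

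- Group 2: "Critical Value = 11FN, (or point estimate > 91.85% with lower 95% CI > 85"%).
- Group 1: "Critical Value = 18 false negative (FN), (or point estimate > 93.3% with lower 95% CI > 89"%).
- Both: "Target Alpha Value = 5%, Power > 95"%.

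Section 7.2 specifies Clopper-Pearson for small samples and "large-sample confidence intervals for samples of greater than 100"; Section 7.4 repeats this for the analysis. Tables 1 and 2 in Section 7.2 list FN limits and intervals for 13 sample sizes, all above 100. Table 1 aims at a lower limit of at least 86%, Table 2 at roughly 90%. Section 7.2 expects 144 positives in Group 2 and, conservatively, 270 in Group 1.

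**The concern.** Containing a target value and clearing a lower threshold are different rules. The first is two-sided: an assay that does too well fails it, and a result beyond the FN limit can still pass. On top of that, the Group 1 threshold is printed with two values, and the interval method named in the text is not the one used in the tables.

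These are the criteria for both primary endpoints. If the Section 7.1 hypotheses are reported, one result could be called met or not met according to which line, or which interval, is picked after the data are seen. The stated probabilities justify the sample size, so they should belong to the rule that is actually used.

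**Working it through.** **Inputs.** Targets, floors, limits and n ranges are from Section 7.1; table entries and expected counts are from Section 7.2.

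**Formulas.** With x positives of n and k = n − x false negatives:

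- Clopper-Pearson: lower = 2.5% quantile of Beta(x, k+1); upper = 97.5% quantile of Beta(x+1, k).
- Wald: p̂ ± 1.96·√(p̂(1−p̂)/n).
- Wilson: [p̂ + z²/2n ± z·√(p̂(1−p̂)/n + z²/4n²)] / (1 + z²/n), z = 1.96.
- Probability of passing: P(FN ≤ k_max), with FN ~ Binomial(n, 1 − target), where k_max is the largest FN count meeting the rule.

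**Step 1: reproduce the plan's figures.** All 13 columns match Clopper-Pearson to rounding. Wald does not match.

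| Result | Printed | Exact | Wilson | Wald |
|---|---|---|---|---|
| 124/135 | 85.9, 95.9 | 85.89, 95.86 | 86.00, 95.39 | 87.24, 96.47 |
| 133/144 | 86.7, 96.1 | 86.74, 96.13 | 86.84, 95.68 | 88.02, 96.70 |
| 252/270 | 89.7, 96.0 | 89.67, 96.00 | 89.71, 95.74 | 90.36, 96.31 |

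The stated probabilities follow from the FN limits at the smallest n: P(FN ≤ 11 | n=135, 95%) = 96.1%, and P(FN ≤ 18 | n=270, 95.34%) = 94.97%.

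**Step 2: containment against the FN limit (exact intervals).**

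- n=270: the interval contains 95.34% for 6 to 20 FN. At 5 FN it is 95.73% to 99.40%, so 0 to 5 FN fail for being too good. At 20 FN it is 88.79% to 95.42%, so 19 and 20 FN pass containment but exceed the limit of 18.
- n=144: the interval contains 95% for 3 to 13 FN. So 0 to 2 FN fail, and 12 and 13 FN pass containment but exceed the limit of 11.
- With the targets true, the two rules disagree in 4.7% of trials at n=270 and 6.8% at n=144.

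**Step 3: the two Group 1 thresholds.** For 252/270, p̂ = 93.33% clears the 93.3% floor. The exact lower limit of 89.67% is above 89% but not above 90%. Wilson gives 89.71%. Wald gives 0.9333 − 1.96·√(0.9333·0.0667/270) = 0.9333 − 0.0298 = 0.9036, above both. The method decides the answer, and two large-sample methods fall on opposite sides of 90%.

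**Step 4: Group 1 probability at 95.34%.**

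| Rule | n=270 | every n, 270 to 300 |
|---|---|---|
| Exact lower limit > 90% | k_max = 17, 91.7% | 89.6% (n=279) to 94.3% (n=292) |
| Wald lower limit > 90% alone | k_max = 18, 95.0% | 94.7% to 97.7% |
| Wald > 90% with the 93.3% floor | k_max = 18, 95.0% | 92.7% to 95.8% |
| Exact > 89% with the 93.3% floor | k_max = 18, 95.0% | 92.7% to 95.8% |

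With an exact limit above 90% the floor never binds, and 95% is not reached at any n.

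**Step 5: Group 2 probability at 95%.** An exact lower limit above 85% alone gives 96.1% to 98.7% over n=135 to 150. Adding the 91.8% floor gives 93.7% (n=146) to 96.7% (n=147), and 94.2% at n=144.

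**Step 6: smaller mismatches.**

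- Table 2, n=280: 261/280 = 93.21%, below the 93.3% floor.
- Table 1, n=135: a lower limit of 85.9%, below its own 86%.
- The Group 2 floor is printed as 91.8% and as 91.85%. At n=147, 135/147 = 91.84%, so the first allows 12 FN (96.7%) and the second 11 (93.4%).

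**The case against.** The primary objectives in Section 3.1.1 and the analysis in Section 7.4 are estimation. No formal declaration of success is planned, and Section 13.4 has no interim analyses or stopping rules. Point estimates do not depend on any of this. That stands, and it limits the consequence.

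Sections 7.2 and 7.4 do call for large-sample intervals above 100. On a Wald reading of the bound alone, the Group 1 probability is about 95%, and 252/270 clears both 90% and 89%. This is a fair reading of those two sentences. But it contradicts the printed tables, and adding the floor from the same Section 7.1 sentence brings the range down to 92.7% to 95.8%.

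A reader might infer that single limits of 18 and 11 FN apply at every n, so that the probability drops to 88.9% at n=300 and 92.6% at n=150. The documents do not support that. Each Critical Value line offers the point-estimate condition as an alternative. It scales with n and gives the tables' 20 FN at n=300 (95.7%) and 12 FN at n=150 (96.1%). The wording is loose, but the intent can be recovered.

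A reader might also infer that the 95% claims fail throughout. They do not. Group 2's bound alone exceeds 95% at every n, adding the floor costs at most 1.3 points, and Group 1's Critical Value line gives 94.97% at n=270.

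**Conclusion.** The plan needs correcting, with modest consequence. Three conflicts stand on the text: containment against a one-directional rule, above 90% against above 89% for Group 1, and large-sample intervals in the text against exact intervals in the tables. One stated probability is clearly off: the 95% for a Group 1 lower limit above 90%, which is 89.6% to 94.3% with the tabulated intervals. Group 2 misses by 0.8 points at the expected n=144 (95 − 94.2) once the floor is applied.

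It would be tempting to conclude that the samples are inadequate or that a poor assay could pass. The figures do not support either. Under the table limits, the chance of passing is at most 1.3% at a true agreement of 85% and at most 4.0% at a true sensitivity of 90%. Read in the printed test orientation, power is therefore above 95% in both groups, as claimed.

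These results assume independent binomial outcomes, true values equal to the Section 7.1 targets, and numbers of positives within the stated ranges.

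**What to change.** 1. Delete both clauses that make containment the evidence. Keep 95% and 95.34% as planning values.
2. In Sections 7.2 and 7.4, name Clopper-Pearson for these proportions. It matches the tables and holds coverage: 97.1% at n=270 and 96.3% at n=144, against 92.9% and 92.7% for Wald. If a large-sample method is kept, name it and recompute Tables 1 and 2.
3. Use one Group 1 rule throughout:
   - (a) Exact lower limit above 90%. Limits at the Table 2 columns become 17, 17, 18, 18, 18, 19, 19 FN. State a probability of 89.6% to 94.3% over n=270 to 300, with 1.5% to 2.4% passing at a true 90%. Six of the seven columns change.
   - (b) Point estimate above 93.3% and exact lower limit above 89%. State 92.7% to 95.8%, with 1.9% to 3.7% passing at a true 90%. Only n=280 changes, to 262 positives and 18 FN.

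   Option (b) is the smaller edit; (a) is needed if a claim of more than 90% is intended.
4. For Group 2, use one floor (91.8%) with an exact lower limit above 85%. State 93.7% to 96.7%, and 94.2% at n=144. Make the 86% in the Table 1 sentence approximate. Simply changing it to 85% would not do: that bound alone gives 11, 12, 12, 12, 13, 13 FN and matches Table 1 only at n=135.
5. Have both Critical Value lines refer to n-specific FN limits.

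The cost is text edits and slightly less favourable stated probabilities. No data, sample or procedure changes. Settle it before Xpert results are compared with culture or routine PCR.

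### Section 7.1 makes the hoped-for accuracy the null and counts a 95% CI containing it as support, so its alpha and power labels are reversed, and in Group 1 this conflicts with its own lower-limit rule

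*Combined protocol and SAP*

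**What the plan says.** For Group 1, section 7.1 states that "we hypothesize that the long term expected sensitivity of HSV DNA using the Xpert HSV 1/2 Assay is 95.34" percent, and takes a 95% confidence interval that contains this value as the evidence for it. That value is the null. The alternative is "Sensitivity < 90" percent, with "Sample Size 270-300" and "Target Alpha Value = 5%, Power > 95" percent.

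The prose of 7.1 also promises a 95% probability that the lower limit of the 95% CI exceeds 90%. The critical-value line uses a different floor: "Critical Value = 18 false negative (FN), (or point estimate > 93.3% with lower 95% CI > 89" percent. Group 2 has the same structure: null 95%, alternative below 85%, 135-150 PCR positives, critical value 11 FN, lower limit above 85%.

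Section 7.2 says that "A 95% confidence interval will be constructed for the sensitivity of Xpert HSV 1/2 Assay relative to culture" in nonpregnant women. Sections 7.2 and 7.4 prescribe large-sample intervals above 100 observations, but the intervals printed in Tables 1 and 2 are Clopper-Pearson. The primary objectives (3.1.1) are worded as estimation, and 7.4 names no hypothesis test for them.

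**The concern.** In a device-accuracy study the error to limit is declaring an assay adequate when its accuracy is at or below the floor. Section 7.1 puts the desired result in the null, so the favourable conclusion is a failure to reject, and the 5% labelled alpha limits the opposite error.

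The containment criterion makes this concrete. A wide interval contains 95.34% easily, so containment is not evidence of adequacy. The lower-limit criterion in the same section runs the other way: requiring the lower limit of a two-sided 95% CI to exceed the floor is a test of accuracy at or below the floor, at nominal one-sided 2.5%. A reader of the final report could apply either criterion to a borderline Group 1 result and reach opposite conclusions, each with support in the text.

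**Working it through.** **Inputs.** Section 7.1: 95.34% and 90% with n 270-300 and 18 FN; 95% and 85% with n 135-150 and 11 FN. Tables 1 and 2: FN limits by n. Let FN be binomial with n trials and probability one minus the true accuracy.

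**1. The plan's own figures (n=270, 18 FN).**
- P(FN > 18 | 95.34%) = 5.03%. This is the stated 5% alpha: the risk of failing a good assay.
- P(FN > 18 | 90%) = 96.3%. This is the stated power above 95%. Its complement, 3.7%, is the chance of passing an assay at the floor.
- Group 2, n=135, 11 FN: P(FN > 11 | 95%) = 3.9% and P(FN > 11 | 85%) = 98.7%.

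The figures reproduce, and they show what the labels mean.

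**2. False acceptance under the printed FN limits (Table 2).**

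| n | 270 | 275 | 280 | 285 | 290 | 295 | 300 |
|---|---|---|---|---|---|---|---|
| FN allowed | 18 | 18 | 19 | 19 | 19 | 19 | 20 |
| P(pass given 90%), % | 3.68 | 2.99 | 3.98 | 3.25 | 2.64 | 2.13 | 2.87 |
| P(fail given 95.34%), % | 5.03 | 5.82 | 4.01 | 4.67 | 5.40 | 6.20 | 4.33 |

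With Table 1's limits (11 FN for n=135-144, 12 FN at n=150), P(pass | 85%) is between 0.6% and 1.3%.

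**3. Containment against the lower limit, Group 1.** With x = n - FN and p = x/n:
- Clopper-Pearson: lower limit = Beta quantile (0.025; x, n-x+1); upper limit = Beta quantile (0.975; x+1, n-x).
- Wald: p ± 1.96 × sqrt(p(1-p)/n).

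At n=270:
- 17 FN: Clopper-Pearson lower limit 90.1%. At 18 FN it is 89.7%, so 17 is the largest count that clears 90%.
- 18 FN: Wald lower limit 90.4%. At 19 FN it falls below 90%.
- 20 FN (250/270): Clopper-Pearson 88.8% to 95.4%, Wald 89.5% to 95.7%. Both contain 95.34% and both miss the 90% floor.
- 21 FN: Clopper-Pearson upper limit 95.1%, which excludes 95.34%; Wald upper limit 95.4%, which contains it.

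Largest FN count that satisfies each rule:

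| n | CP contains 95.34% | CP lower > 90% | Wald contains 95.34% | Wald lower > 90% |
|---|---|---|---|---|
| 270 | 20 | 17 | 21 | 18 |
| 280 | 20 | 18 | 21 | 19 |
| 290 | 21 | 18 | 22 | 20 |
| 300 | 22 | 19 | 23 | 21 |

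Over all 31 values of n the cut-offs are 20-22 against 17-19 (Clopper-Pearson, 2-3 FN apart) and 21-23 against 18-21 (Wald, 1-3 FN apart). They never coincide.

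At n=270 and true sensitivity 90%, containment accepts with probability P(FN ≤ 20) = 9.0% (Clopper-Pearson) or P(FN ≤ 21) = 13% (Wald). The very low FN counts at which the interval lies wholly above 95.34% have negligible probability here. They show another oddity: with 5 or fewer FN of 270 (265/270 = 98.1%) the Clopper-Pearson interval excludes 95.34%, so an excellent result fails the containment criterion.

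**4. Group 2.** With Clopper-Pearson, containing 95% and a lower limit above 85% give the same cut-off at 13 of the 16 values of n from 135 to 150, and differ by 1 FN at n=135, 142 and 143.

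**5. Operating characteristics with the floor in the null.** Success means the lower two-sided 95% limit is above the floor.
- Group 1, Clopper-Pearson: alpha at 90% is 1.5-2.4%; power at 95.34% is 89.6-94.3%. The stated 95% probability is not reached at any planned n.
- Group 1, Wald, lower-limit condition alone: power 94.7-97.7%; actual alpha 3.4-5.3%, above the nominal 2.5%.
- Group 2, Clopper-Pearson: alpha at 85% is 1.3-2.4%; power at 95% is 96.1-98.7%.

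**The case against.** The best defence is that both errors are already limited, only under unconventional names. With the alternative at the floor, power above 95% means false acceptance below 5%, and step 2 confirms this for every printed FN limit. That stands: a reader might infer that the plan leaves false acceptance uncontrolled, and the printed limits do not support that.

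A reader might also infer that testing 95.34% at one-sided 5% and requiring a lower limit above 90% give different decisions at every planned n. That depends on the method. An exact 5% test allows 19-20 FN and never matches the Clopper-Pearson floor, but it agrees with the Wald floor, the method the text prescribes above 100, at 21 of 31 n. The printed 18 FN agrees with the Clopper-Pearson floor at n=280-291. Only the containment rule conflicts with the 90% floor at all 31 n under both methods.

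A third tempting reading is that a shortfall in comparator positives would let a poor assay through. That uses non-rejection alone, whereas 7.1 also prints a CI floor, which becomes harder to meet as n falls. For Group 2, stored specimens are kept in reserve to secure enough positives (section 4).

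Finally, the objectives are estimation and 7.4 tests nothing for the primary measures, so no primary estimate or interval would change. This limits the practical weight. But 7.1 prints hypotheses, critical values, alpha and power for both primary measures, and a reader will use them to judge the result.

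**Conclusion.** The point holds. The fault lies in the direction of the hypotheses, the labels on the two error rates and the containment criterion, not in the printed FN limits. In Group 1, containment and the lower-limit rule disagree by 1-3 FN at every n from 270 to 300, and containment would accept a 90% assay with probability 9% or 13% at n=270. The promised 95% probability of clearing 90% becomes 89.6-94.3% with the intervals that Table 2 actually uses. Group 2 is affected little.

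This rests on exact binomial calculation, a 90% Group 1 floor (the prose and the alternative, not the 89% in the critical-value line) and two-sided 95% limits. The Wald power figures do not add the separate point-estimate condition in 7.1. The correction should be made, but it does not threaten the primary estimates.

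**What to change.** Reword section 7.1:
- Group 1: null sensitivity ≤ 90%, alternative > 90%. Group 2: null positive percent agreement ≤ 85%, alternative > 85%.
- Define success as the lower limit of the two-sided 95% CI above the floor (one-sided 2.5%).
- Label 95.34% and 95% as the values assumed for power.
- Delete the clause that takes an interval containing the hypothesised value as evidence for it.
- Reconcile the 89% and 90% floors, and the interval method across 7.1, 7.2 and 7.4.
- Replace the alpha and power line with the figures in step 5 for the method chosen. If Wald is kept, state that its actual alpha in Group 1 exceeds 2.5%.

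If 7.1 is not meant to govern any conclusion, the alternative is to remove the hypotheses, alpha and power and keep the precision argument of 7.2.

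The cost is text only: no new participants, tests or data. The downside is a slightly less favourable stated power for Group 1 under Clopper-Pearson, about 90-94% in place of above 95%.
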